3.11 Definition of Subjects Lost to Follow-up

Subjects, or the subject's parent/guardian who cannot be contacted on or before their final visit prior to the trial termination date, who do not have a known reason for discontinuation (eg, withdrew consent or AE) and for whom a current health status at the end of the trial cannot be determined will be classified as "lost to follow-up" as the reason for discontinuation. Current health status can be determined from a variety of sources, either by obtaining acceptable documentation for death (ie, death certificate, medical records, public records, or statement by a family member or primary care physician) or acceptable documentation for life (ie, direct contact with the subject, medical records, successful telephone contact with the subject, statement by a family member or primary care physician, or public records). It is expected that 3 documented attempts will be made to determine a subject's current health status before assigning a "lost to follow-up" status.

3.12 Subject Compliance

Subject compliance will be monitored by pill counts as IMP is returned. Any subject who, without the instruction of the investigator, discontinues tolvaptan investigational product, discontinues tolvaptan for 30 consecutive days or misses > 30% of the doses intended for a period between visits (whichever is greater) will be deemed noncompliant. Depending on the circumstances leading to noncompliance, the subject may be withdrawn from the trial or discontinued from investigational product administration by the investigator and/or sponsor. It is preferred that subjects who discontinue tolvaptan, or are withdrawn by the investigator for reasons other than noncompliance or lost to follow-up, will continue with regularly scheduled visits completing all procedures as provided in the protocol.

Protocol 156-13-211

3.13 Protocol Deviations

This trial is to be conducted as described in this protocol. In the event of a significant deviation from the protocol due to an emergency, accident or mistake (eg, violation of informed consent process, IMP dispensing or subject dosing error, subject enrolled in violation of eligibility criteria or concomitant medication criteria), the investigator or designee must contact the sponsor at the earliest possible time. This will allow an early joint decision regarding the subject's continuation in the trial. This decision will be documented by the investigator and the sponsor, and reviewed by the site monitor.

4 Restrictions

4.1 Prohibited or Restricted Medications

Medications or surgical therapies used for the purpose or potential for modifying the progression of PKD cyst growth or development will be prohibited. These include, but are not restricted to, somatostatin agonists, rapamune (sirolimus), anti-sense ribonucleic acid therapies, vasopressin antagonists other than tolvaptan, (eg, OPC-31260 (mozavaptan), Vaprisol (conivaptan), agonists (eg, desmopressin) and cyst decompression surgery.

Continuous or short-term use of other medications, while not prohibited, may be restricted by the investigator because of their potential for interference with tolvaptan metabolism (see [Section 3.2.1](#) and [Section 3.2.2](#)).

A partial list of strong and moderate CYP3A4 inhibitors can be found in [Table 4.1-1](#) below:

Table 4.1-1 Strong and Moderate CYP3A Inhibitors (partial list)

amprenavir	atorvastatin	aprepitant	chloramphenicol (if used orally)
cimetidine	clarithromycin	clotrimazole (if used orally)	danazol
delavirdine	diltiazem	erythromycin	fluconazole
fluvoxamine	indinavir	isoniazid	itraconazole
josamycin	ketoconazole (if used orally)	nelfinavir	nefazadone
quinupristin/ dalfopristin	ritonavir	saquinavir	troleandomycin
verapamil	Seville orange products	grapefruit products	

Protocol 156-13-211

Pharmacodynamic interactions are a consideration for the use of diuretics, which may be only used intermittently, and not within 7 days of a urine assessment. Diuretics are not generally recommended in ADPKD due to their tendency to increase AVP levels through relative dehydration or volume depletion; thus, chronic use of diuretics (eg, for hypertension) will be prohibited and is an exclusionary criterion for this trial.

Some drugs are known to alter creatinine concentrations so, while not prohibited, subjects should alert their trial doctor, and any other health-care providers, to take this into consideration when considering changes in their prescribed or over-the-counter medications. A list would include: non-steroidal anti-inflammatory drugs like aspirin or ibuprofen, chemotherapy drugs, cephalosporin, the combination of elvitegravir, cobicistat, emtricitabine, and tenofovir (Stribild™), dolutegravir, dronedarone, ranolazine, metformin, and trimethoprim.

4.2 Dietary Restrictions and Recommendations

Restriction of excess dietary sodium and cooked meat protein may prove beneficial to subjects with a history of, or predisposition for, hypertension or kidney disease in general and should be applied to all subjects diagnosed with advanced ADPKD, particularly if there is evidence for a propensity for rapid progression. In the absence of alternate regional practices, dietary salt < 5g/day, dietary cooked meat protein < 1 g/kg/day and a limit on caffeinated drinks/foods should also be given (no more than 2 coffee equivalents per day). A history of alcohol and smoking intake will be collected at screening. Alcohol and tobacco consumption should be avoided or minimized as much as possible.

Additionally, fluid intake is generally encouraged in subjects with PKD. Given the potential for dehydration with tolvaptan treatment, all subjects should be instructed to ingest fluids in anticipation of, or at the first sign of thirst in order to avoid excessive thirst or dehydration. Upon consent, all subjects should receive the recommendation to ingest at least 2 to 3 liters of fluid (including in solid, semi-solid, and liquid foods) per day, unless otherwise directed by their trial doctor. This recommendation should start during screening and continue through the end of the trial. Additionally, subjects should ingest 1 to 2 cups of water before bedtime regardless of perceived thirst, and replenish fluids overnight with each episode of nocturia. Dehydration will be monitored by subject self-assessment of changes in body weight and reporting of symptoms. Acute changes of > 3% of body weight (increase or decrease) over any 7-day period should be noted. Subjects should be instructed to report acute changes in body weight to the trial physician for further evaluation and recommendations.

Protocol 156-13-211

Subjects should be advised that the ingestion of pomelo, grapefruit, or Seville orange products would be expected to increase tolvaptan concentrations and these should be avoided. In the event of an unintentional ingestion of such products, the investigator may ask the subject to temporarily interrupt the IMP.

5 Reporting of Adverse Events

The following describes the methods and timing for assessing, recording, and analyzing safety parameters, as well as the procedures for eliciting reports of and recording and reporting AEs and intercurrent illnesses and the type and duration of the follow-up of subjects after AEs.

Medical follow up is expected for AEs which lead to discontinuation which are serious, or which are of special interest (eg, liver abnormalities, skin neoplasms, glaucoma).

ADPKD is a progressive disorder involving the kidney, liver and occasionally other organ systems. A number of AEs may be associated with this disorder including urine concentration defects, hypertension, renal pain, renal infection, nephrolithiasis, hematuria, and ESRD. As such, these events are considered “expected” in this trial population and will not qualify for the purposes of regulatory expedited reporting (eg, Suspected Unexpected Serious Adverse Reaction and investigational new drug [IND] safety reports).

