6.6 Protocol Deviations

Protocol deviations occurring to patients will be listed and summarized (only for major protocol deviations) by patient type by parent trial.

7 Efficacy Analysis

No efficacy analyses are planned.

8 Safety Analyses

Safety analysis will be conducted based on the Safety Population, which is defined as all subjects in the Enrolled Population who take at least one dose of IMP. Safety variables to be analyzed include clinical laboratory tests, vital signs, and AEs. CCI [REDACTED]

In general, baseline measurements of safety variables are defined as the last measurements prior to the first dose of IMP in Trial 156-13-211. Safety variables will be summarized by descriptive statistics, (eg, proportion, mean, median, SD, minimum, and maximum values). Summary statistics, including changes from baseline, will be provided for safety variables based on all available data. No inferential statistical analyses of the safety variables will be performed.

Safety variables to be analyzed include:

- Adverse events
- Vital signs
- Clinical laboratory assessments
- Serum transaminase elevations for frequency (2x, 3x, 5x and 10x ULN), time to onset, time to peak levels, time of offset (< 3x, 2x, or 1x ULN), response to de-challenge and re-challenge and frequency of progression to Hy's laboratory criteria (ALT or AST > 3x ULN and bilirubin, total (BT), > 2x ULN without alkaline phosphatase > 2x ULN)
- Serum sodium excursions above 145, 150, or 155 mmol/L or below 136, 130, or 125 mmol/L

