8.3 Vital Signs Data

Summary statistics for changes from baseline in vital signs and potentially clinically significant results in vital signs will be summarized by parent study (and prior treatment).

Incidence of potentially clinically significant vital sign results will be summarized by parent study (and prior treatment). Criteria of potentially clinically significant vital sign abnormalities are provided in [Appendix 2](#).

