Appendix 2 Criteria of Potentially Clinically Significant Vital Sign Abnormalities

Test Type	Test Parameters	Unit	Sex	Criteria (meet either one will count)	
				Limit	Change from baseline
VITAL SIGNS	SBP, SITTING	mmHg	Male/Female	≥ 180	≥ 20
VITAL SIGNS	SBP, SITTING	mmHg	Male/Female	≤ 90	≤ -20
VITAL SIGNS	DBP, SITTING	mmHg	Male/Female	≥ 105	≥ 15
VITAL SIGNS	DBP, SITTING	mmHg	Male/Female	≤ 50	≤ -15
VITAL SIGNS	HEART RATE	bpm	Male/Female	≥ 120	≥ 15
VITAL SIGNS	HEART RATE	bpm	Male/Female	≤ 50	≤ -15
VITAL SIGNS	TEMPERATURE	degree C	Male/Female	≥ 38.3	≥ 1.1
VITAL SIGNS	WEIGHT	kg	Male/Female		≥ 7 percent

This page is a manifestation of an electronically captured signature

SIGNATURE PAGE

Document Name: P15613211_SAP

Document Number: 0001251745

Document Version: 2.0

Signed by	Meaning of Signature	Server Date (dd-MMM- yyyy hh:min) - UTC timezone
PPD	Safety Approval	31-Oct-2018 22:22:05
	Clinical Approval	06-Nov-2018 16:20:29
	Biostatistics Approval	31-Oct-2018 23:59:21

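### SAP Appendix 2 has no decrease row for body weight, so the table of potentially clinically significant vital signs, read by its own sign convention, counts weight gain but not weight loss

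*Protocol*

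**What the plan says.** Protocol 4.2 introduces its fluid advice with the words "Given the potential for dehydration with tolvaptan treatment". It goes on: "Dehydration will be monitored by subject self-assessment of changes in body weight and reporting of symptoms", then "Acute changes of > 3% of body weight (increase or decrease) over any 7-day period should be noted", and finally "Subjects should be instructed to report acute changes in body weight to the trial physician for further evaluation and recommendations". Separately, post-void body weight is a scheduled vital sign, recorded in clinic at every visit (Protocol Table 3.7-1, footnote on vital signs).

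SAP 8.3 plans two outputs for vital signs. One is descriptive and is split according to the parent trial and the treatment received there: "Summary statistics for changes from baseline in vital signs and potentially clinically significant results in vital signs will be summarized". SAP section 8 gives the statistics: "Safety variables will be summarized by descriptive statistics, (eg, proportion, mean, median, SD, minimum, and maximum values"). The other is a threshold count: "Incidence of potentially clinically significant vital sign results will be summarized by parent study (and prior treatment"), using the criteria in Appendix 2.

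Appendix 2 has two criterion columns, an absolute limit and a change from baseline, under the rule "Criteria (meet either one will count"). Sitting systolic pressure, sitting diastolic pressure and heart rate each take two rows, one for increase and one for decrease. Temperature takes one row and weight takes one row. The weight row leaves the limit blank and sets the change from baseline at ≥ 7 percent.

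**The concern.** Long-term safety is the trial's only objective, and SAP 8.3 is where the plan counts subjects whose vital signs cross a pre-set threshold. For weight, the only threshold appears to point upward, while the fluid risk that the protocol names would show as a fall.

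At stake is one line of a descriptive safety table. As written, the table could report how many subjects gained 7 percent or more and be silent on how many lost as much. A reader of the final report could take that silence as an absence of marked weight loss.

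**Working it through.** The SAP states no figure to reproduce here. The check is a reading of the table, followed by an illustration of scale.

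**Step 1: the sign convention in Appendix 2 (change from baseline).**

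| Parameter | Increase row | Decrease row |
|---|---|---|
| Systolic pressure, sitting | ≥ 20 mmHg | ≤ -20 mmHg |
| Diastolic pressure, sitting | ≥ 15 mmHg | ≤ -15 mmHg |
| Heart rate | ≥ 15 bpm | ≤ -15 bpm |
| Temperature | ≥ 1.1 °C (limit ≥ 38.3) | none |
| Weight | ≥ 7 percent (no limit) | none |

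Where a decrease counts, the table gives it its own row with a minus sign. Temperature, the only other single-row parameter, clearly means an increase. A programmer following this pattern would code weight as signed change ≥ 7 percent.

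**Step 2: apply the row to example changes.**

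| Weight change | Row as written (signed) | Two rows (≥ 7 or ≤ -7) | Size above the protocol's 3 percent |
|---|---|---|---|
| -15% | not flagged | flagged | yes |
| -10% | not flagged | flagged | yes |
| -7% | not flagged | flagged | yes |
| -3.5% | not flagged | not flagged | yes |
| +7% | flagged | flagged | yes |
| +10% | flagged | flagged | yes |

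The last column compares size only. The protocol item also requires the change to occur within 7 days, which a change from baseline does not show. The -3.5% line shows that a mirrored 7 percent row is not a substitute for that item.

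**Step 3: scale, under stated assumptions.** Inputs: N = 2,500, the expected enrolment in SAP section 4. Percent weight change at one visit is assumed normal with mean m and standard deviation SD. Neither is given in the documents.

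Subjects at or below -7 percent = N × Φ((-7 - m)/SD).

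With m = 0:

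- SD 3: Φ(-2.33) = 0.010, about 25 subjects
- SD 4: Φ(-1.75) = 0.040, about 100
- SD 5: Φ(-1.40) = 0.081, about 202
- SD 6: Φ(-1.17) = 0.122, about 304
- SD 7: Φ(-1.00) = 0.159, about 397

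The result depends on the assumed mean. Over SD 3 to 6, m = -1 percent gives 57 to 397 subjects, and m = +1 percent gives 10 to 228.

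The share of large changes that are losses also depends on it. With m = 0 it is one half. At SD 5, m = +1 gives 137 losses among 425 changes of 7 percent or more (137/425 = 32 percent), and m = -1 gives 288 of 425 (68 percent).

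**The case against.** The strongest reply is that weight loss is not invisible in this plan. SAP 8.3 also summarises change from baseline, and weight is one of the vital signs. A general downward shift would move the mean and median, and the largest loss would appear as the minimum. Dehydration or weight loss recorded as an adverse event enters the adverse event tables. Serum sodium excursions above 145, 150 and 155 mmol/L, a laboratory measure closer to fluid status, are tabulated under SAP 8.4. All of this stands. A reader might infer from Appendix 2 that weight loss is counted nowhere, and the documents do not support that. What these outputs lack is the number of subjects with a loss of 7 percent or more. A mean and SD do not give it, a minimum describes one subject, and adverse event capture depends on someone reporting an event.

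A second reply is that Protocol 4.2 and Appendix 2 measure different things: a self-assessed change over 7 days, reported to the trial physician, against a clinic-visit change from baseline with no time limit. This also stands. A reader might infer that the SAP contradicts the protocol's 3 percent item, but nothing says Appendix 2 is meant to implement it. Protocol 4.2 shows only that the sponsor regards both directions of weight change as relevant.

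Third, a slow 7 percent loss is not specific to dehydration. Subjects from Trial 156-08-271 retain their last dose, and baseline is the last value before the first dose in this trial, so their baseline may already be on drug. That limits what a loss row could say about dehydration. It does not explain counting gain and omitting loss.

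Fourth, the weight row is the only one expressed in percent and the only one without a limit, so a magnitude may have been intended. This cannot be excluded. In that case losses would be counted, but pooled with gains in one figure.

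**Conclusion.** The point holds in limited form. Under the table's own convention, the incidence table in SAP 8.3 counts weight gain of 7 percent or more and omits loss of the same size. Under the alternative reading it mixes the two. Either way, the SAP does not deliver a count of subjects with marked weight loss.

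The size is unknown because the documents give no distribution of weight change. The figure of about 25 to 397 of 2,500 subjects rests on a normal distribution with mean 0, SD 3 to 7 percent, one visit and all expected subjects contributing. It is not an estimate of dehydration cases. A reader might infer that half of all large weight changes are missed. That holds only if changes are symmetric about zero, which the documents do not say.

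The consequence is confined to a descriptive table. SAP section 8 plans no inferential safety analysis, and no test depends on this row. The weights are collected in any case, so a loss count could still be produced later, but it would not be pre-specified. The change is worth making because it costs almost nothing and fills a gap in the trial's only area of analysis.

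**What to change.** In SAP Appendix 2, replace the single weight row with two rows at the sponsor's existing cut-off: increase from baseline ≥ 7 percent, and decrease from baseline ≤ -7 percent. In SAP 8.3, tabulate the two separately by parent study and prior treatment. This also removes the doubt about sign.

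The cost is one extra appendix row and one extra line in a planned table. No new data are needed, since post-void weight is already recorded at each visit, and clinical management does not change. The SAP should not present the decrease row as implementing the protocol's separate 7-day self-monitoring item, which it would not do.

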5.1 Definitions

An AE is defined as any untoward medical occurrence associated with the use of an IMP in humans, whether or not considered IMP related.

A suspected adverse reaction means any AE for which there is a reasonable possibility that the IMP caused the AE. For the purpose of IND safety reporting, “reasonable possibility” means there is evidence to suggest a causal relationship between the IMP and the AE. Suspected adverse reaction implies a lesser degree of certainty about causality.

A serious adverse event (SAE) includes any event that results in any of the following outcomes:

1. Death
2. Life-threatening, ie, the subject was, in the opinion of the investigator, at immediate risk of death from the event as it occurred. It does not include an event that, had it occurred in a more severe form, might have caused death.

Protocol 156-13-211

3. Persistent or significant incapacity or substantial disruption of the ability to conduct normal life functions.
4. Requires inpatient hospitalization or prolongs hospitalization
NOTE: A pre-scheduled hospitalization is not considered an SAE.
5. Congenital anomaly/birth defect
6. Other medically significant events that, based upon appropriate medical judgment, may jeopardize the subject and may require medical or surgical intervention to prevent one of the outcomes listed above, eg, allergic bronchospasm requiring intensive treatment in an emergency room or home, blood dyscrasias or convulsions that do not result in hospitalization, or the development of drug dependency or drug abuse.

Nonserious AEs are all AEs that do not meet the criteria for a "serious" AE.

Immediately Reportable Event (IRE):

- Any SAE
- Any AE (whether serious or nonserious) that necessitates discontinuation of IMP.
- Any subject with a new liver test abnormality meeting the AE (whether serious or nonserious) or laboratory threshold criteria (whether considered an AE or not) for hepatic eCRF reporting.
- Any subject reporting an AE of special interest (eg, skin neoplasms or glaucoma).
- Pregnancies are also defined as IREs. Although normal pregnancy is not an AE, it will mandate IMP discontinuation and must be reported on an IRE form to Otsuka Pharmaceutical Development & Commercialization, Inc. (OPDC). Pregnancy will only be documented on the AE eCRF if there is an abnormality or complication.
- Additionally, in the EU region, events involving overdose, misuse and abuse as well as reported lack of efficacy must also be reported as IREs.

Clinical Laboratory Changes: It is the investigator's responsibility to review the results of all laboratory tests as they become available. This review will be documented by the investigator's dated signature on the laboratory report. For each abnormal laboratory test result, the investigator needs to ascertain if this is an abnormal (ie, clinically significant) change from baseline for that individual subject. This determination, however, does not necessarily need to be made the first time an abnormal value is observed. The investigator may repeat the laboratory test or request additional tests to verify the results of the original laboratory tests. If this laboratory value is determined by the investigator to be an abnormal change from baseline for that subject, this is considered an AE.

Severity: Adverse events will be graded on a 3-point scale and reported as indicated on the CRF. The intensity of an adverse experience is defined as follows:

Protocol 156-13-211

- 1 = Mild:** Discomfort noticed, but no disruption to daily activity.
2 = Moderate: Discomfort sufficient to reduce or affect normal daily activity.
3 = Severe: Inability to work or perform normal daily activity.

IMP Causality: Assessment of causal relationship of an AE to the use of the IMP:

- Related:** There is a reasonable probability or possibility of a temporal and causal relationship between the IMP and the AE.
Not Related: There is no temporal or causal relationship to the IMP administration.

5.2 Eliciting and Reporting Adverse Events

The investigator will periodically assess subjects for the occurrence of AEs. In order to avoid bias in eliciting AEs, subjects should be asked the following non-leading question: "How have you felt since your last visit?" All AEs (serious and nonserious) reported by the subject must be recorded on the source documents and eCRFs provided by the sponsor.

In addition, Quintiles (drug safety service) must be notified immediately by telephone or fax of any immediately reportable events according to the procedure outlined below in [Section 5.3](#). Special attention should be paid to recording hospitalization and concomitant medications.

